8.2.1.10. Response Evaluation Visits

Response assessments will be performed every 4 Cycles or 16 weeks (± 7 days) starting at Cycle 5 until completion of the Cycle 37 Visit and then every 6 Cycles or 24 weeks (± 7 days) thereafter until Treatment Termination. All visits will be scheduled in relation to Cycle 1 Day 1. Visit windows are relative to the Cycle 1 Day 1 visit date.

Response assessment visits on an every 16-week schedule will occur as follows: Cycle 5, 9, 13, 17, 21, 25, 29, 33, and 37. Response assessment visits on an every 24-week schedule will begin with Cycle 43 and continue every 6 cycles as follows: Cycle 49, 55, 61, 67, 73, 79, 85, 91, 97, 103, etc.

The following procedures will be performed:

- PRO assessment
- Limited symptom-directed physical exam including weight and eye-related symptom assessment and evaluation of lymphatic system, liver and spleen.
- Evaluation of ECOG performance status
- Vital signs
- B-symptom assessment
- Review of AEs and concomitant medications
- Collect blood and urine samples for the following clinical laboratory tests:
 - Hematology
 - Serum chemistry
 - Urine pregnancy test (every 8 weeks from Day 1 [or at the closest associated visit] for women of reproductive potential only)
- Drug accountability
- Dispense study drug
- Imaging by CT/MRI
- Overall response assessment
- To confirm a suspected CR:
 - Imaging by PET to confirm CR if screening PET was positive

- Bone marrow core biopsy, or aspirate if core biopsy not possible, to confirm CR (local testing and if samples available, potentially central) as well as aspirate for central MRD assessment, if there was evidence of lymphoma involvement in the bone marrow at baseline by histology
- For subjects achieving a CR, research laboratory blood sample collected for:
 - Determination of MRD by peripheral blood assessment is repeated at each response evaluation visit after CR is achieved

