Endpoint	Definition	Analysis Method
Exploratory Endpoints		
CR30	The proportion of subjects achieving a best overall response of CR per investigator assessment at or prior to 30 months and at or prior to initiation of subsequent anti-cancer therapy.	Chi-square test, rate ratio and 95% CI. For each treatment, Clopper-Pearson method is used for 95% CI of the estimated proportion.
MRD negativity rate	The proportion of follicular lymphoma subjects who achieve a CR and who reach MRD-negative disease status.	Chi-square test or Fisher's exact test depending on the sample size, rate ratio and 95% CI for each treatment (Clopper-Pearson method).
FACT-Lym total score and subscale scores	Change from baseline by visit regardless of initiation of subsequent anti-cancer therapy, proportion of subjects achieving clinically meaningful improvement or worsening on or prior to initiation of subsequent anti-cancer therapy, time to improvement or worsening on or prior to initiation of subsequent anti-cancer therapy. Clinically meaningful improvement is defined as an increase from baseline $\geq 7$ points for FACT-Lym total score, ( $\geq 6$ points for Trial Outcome Index, $\geq 3$ points for lymphoma subscale score). Clinically meaningful worsening is defined as a reduction from baseline $\geq 5$ points for lymphoma subscale score, ( $\geq 6$ points for Trial Outcome Index.)	
Descriptive summary statistics. The proportion of subjects achieving clinically meaningful improvement or worsening will be compared between the two randomized treatment arms using chi-square test. 95% CI for the rate ratio will be calculated. For each parameter, change from baseline will be analyzed using the Mixed-Effects Model Repeated Measure (MMRM). The model includes the continuous baseline scores, and categorical fixed effects of pre-specified stratification factors, treatment, time point and treatment-by-time point interaction. An unstructured variance covariance matrix will be used. Kenward-Roger's approximation will be used to estimate denominator degrees of freedom. The 2-sided 95% CIs will be calculated for the least square means.
 
Time to event analyses will be conducted for the time to improvement/worsening endpoints. Subjects who have not met the definition of improvement/worsening will be censored at the last non-missing post-baseline PRO assessment prior to or on the date of initiating subsequent anti-cancer therapy.

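### The chi-square on whole-period FACT-Lym improvement and worsening proportions favours whichever arm stays on treatment longer; the inflation is modest and the endpoint exploratory

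*SAP*

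**What the plan says.** The FACT-Lym row of SAP Table 6 lists three kinds of outcome: change from baseline by visit, the "proportion of subjects achieving clinically meaningful improvement or worsening on or prior to initiation of subsequent anti-cancer therapy", and time to improvement or worsening. On the Lym subscale, improvement is a rise of at least 3 points and worsening a fall of at least 5. For the proportions, no visit, window or confirmation rule is given, nor a rule for subjects without questionnaires. The arms "will be compared between the two randomized treatment arms using chi-square test", and a 95% CI for the rate ratio is added.

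The same cell plans a time-to-event analysis: "Subjects who have not met the definition of improvement/worsening will be censored at the last non-missing post-baseline PRO assessment" up to the start of new therapy. It also plans a mixed model for repeated measures on change from baseline.

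Protocol Appendix A and Sections 8.2.1.1, 8.2.1.6, 8.2.1.7, 8.2.1.10 and 8.2.2 schedule the questionnaire at Cycle 1 Day 1, Cycle 3 Day 1, each Response Evaluation Visit, and the suspected-PD/termination visit. Section 8.2.1.10 sets the interval: "Response assessments will be performed every 4 Cycles or 16 weeks (± 7 days) starting at Cycle 5" through Cycle 37, "then every 6 Cycles or 24 weeks (± 7 days) thereafter until Treatment Termination". Off-treatment response follow-up (Section 8.3.1) lists no questionnaire. Protocol 10.6.3 says only that these proportions are summarized by arm.

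**The concern.** With no window, the natural reading is that a subject counts as improved, or as worsened, if any post-baseline questionnaire before new therapy crosses the threshold. The chance of that grows with the number of questionnaires completed, even if scores only fluctuate around a constant level. Questionnaires stop when treatment stops, and treatment runs to progression or toxicity. The number of chances is therefore set largely by time to progression or discontinuation, and the trial is designed on the expectation that time to progression differs.

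A chi-square gives every subject equal weight regardless of observation time. The two proportions can then differ with no quality-of-life effect, with improvement and worsening both pushed up in the same arm. A reader of the p-value or rate ratio could not separate that from a real effect. Protocol 7.1.1.13 names the Lym subscale as the one of most interest, so the result is likely to be read.

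**Working it through.** **Inputs from the documents.** Control median PFS 28 months, HR 0.60, 200 events, 445 subjects at 3:1 (about 334 vs 111), primary PFS analysis at about 77 months, thresholds of +3 and -5, and the questionnaire schedule above.

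**Reproducing the plan's figure.** No power, SD or responder rate is stated for FACT-Lym. The PFS assumption behind the difference in time on treatment does reproduce. Power = Φ(√(200 × 0.75 × 0.25) × |ln 0.60| − 1.96) = Φ(6.124 × 0.511 − 1.96) = Φ(1.17) = 87.9%. With 1-sided alpha 0.024 it is 87.5%. The SAP states about 87%. The implied Arm A median is 28/0.60 = 46.7 months.

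**Null simulation.** Exponential time on treatment with medians 46.7 and 28 months; the score distribution is identical in both arms; chi-square at an assumed 2-sided 0.05. Two sets of assumptions were used, neither taken from the documents for the scores:

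| | Set 1 | Set 2 |
|---|---|---|
| Follow-up | uniform, 35-77 months | 60 months |
| SD of change | total 6-10, within-subject correlation 0.4-0.8 | 4-6 between, 4-6 within subject |
| Mean questionnaires, A vs B | 10.2 vs 8.6 | 10.5 vs 8.9 |
| Null rejection | worsening 6-14%; improvement 6-12% (correlation 0.6-0.8) | about 9-19% |

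In Set 1 the proportion ever worsened is 2 to 4.5 points higher in Arm A (63% vs 60% at SD 8, correlation 0.6). In Set 2 with SDs 4 and 4, improvement is about 76% vs 72%. The termination-visit questionnaire must be counted. Leaving it out gives 9.9 vs 8.1 questionnaires, and rejection for improvement at SDs 4 and 4 rises from about 12% to 18%.

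**Isolating the cause.** With equal time on treatment (28 months in both arms) rejection is 5%.

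**Dependence on other discontinuation.** The monthly progression hazard is ln 2/28 = 0.0248 in Arm B and 0.60 × 0.0248 = 0.0149 in Arm A, a difference of 0.0099. The bias therefore cancels when Arm A loses about 1 percentage point more per month for other reasons.
- 1.5% vs 0.5% per month (A vs B): 5% rejection.
- 15% vs 5% per year: 8.2 vs 8.1 questionnaires, 5%.
- 30% vs 5% per year: 6.6 vs 8.1 questionnaires, 11%, with Arm B higher.

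**Alternatives on null data.**
- Log-rank on time to first improvement or worsening, censored at the last questionnaire as planned: about 4-7% (600 trials, simulation error about 0.9 points).
- Chi-square at Cycle 13 among subjects assessed: about 4-6%.
- Chi-square at Cycle 25, counting missing subjects as not improved: about 17-19%. Cycle 25 Day 1 falls at 24 × 28 = 672 days, or 22.1 months. The fraction still progression-free is 2^(−22.1/46.7) = 72% in Arm A and 2^(−22.1/28) = 58% in Arm B. With SDs 4 and 4 and scores rounded to integers, the chance of a 3-point rise at one visit is P(Z > 2.5/√32) = 33% in both arms. The compared proportions are then 0.33 × 0.72 = 24% and 0.33 × 0.58 = 19%, a gap due entirely to PFS.

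**The case against.** The strongest reply is that unequal follow-up is already handled in the same table cell. The time-to-event analysis censors at the last questionnaire, and the mixed model works visit by visit. FACT-Lym is exploratory and outside the tested sequence of PFS, ORR, OS and infusion-related reactions. SAP Section 2 reports exploratory results only where they are clinically meaningful. All of that stands. It limits the consequence but does not make the chi-square valid. It also means that dropping the test costs little, because a near-nominal comparison is already planned.

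A second reply is that counting any crossing before new therapy is an inference from the missing window. That is true, but the cell offers no other reading. CR30 in the same table shows that a window is written where one is intended.

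A reader might infer that the test will show a difference with no effect, or that the trial's quality-of-life results as a whole reflect exposure time. Neither is supported. Under the assumptions tried, most null trials do not reject; size and direction depend on discontinuation rates the documents do not give; and the other two analyses do not share this flaw. Nor is it an error that one subject can count as both improved and worsened, because these are separate proportions.

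**Conclusion.** The point holds as a minor one. Followed as written, the chi-square and rate-ratio interval compare proportions built on unequal numbers of chances. Under the design hazard ratio, the false-positive rate is roughly 6-19% against a nominal 5%, usually with both proportions higher in Arm A. That range rests on assumed SDs and correlations, exponential times, and treatment ending at progression. It falls to 5% or reverses when other discontinuation is sufficiently higher in Arm A. Type I error control for the primary and key secondary endpoints is unaffected.

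The near-nominal behaviour of the log-rank assumes that censoring is unrelated to quality of life. If subjects stop because they are deteriorating, that analysis needs its own sensitivity check.

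**What to change.** In SAP Table 6:

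1. Remove the chi-square and rate-ratio CI for the whole-period improvement and worsening proportions. Report them descriptively with the number of questionnaires completed by arm. This fits Protocol 10.6.3.
2. Name the planned time-to-improvement/worsening analysis as the between-arm comparison, with a sensitivity analysis treating PD, death or discontinuation as competing events.
3. If a responder comparison is kept, define it at fixed scheduled visits (for example Cycle 13) among subjects with an assessment, and show the number assessed by arm.
4. Do not count subjects missing because of PD or discontinuation as not improved unless the result is labelled a composite endpoint, since that rule puts the PFS difference back into the comparison.

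The cost is SAP wording and table shells, with no new data. The whole-period proportions lose their p-value, and the fixed-visit analysis is conditional on remaining on treatment, which should be stated beside it.

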#### 4.1 Exploratory Efficacy Analyses

Analyses of PFS, DOR, TTP, and DOCR for the following:

- subjects who discontinued ibrutinib for any reason other than PD vs. who did not discontinue ibrutinib
- subjects who discontinued ibrutinib for any reason other than PD after achieving BOR of SD or PR vs. CR
- subjects by ibrutinib treatment duration (< 24 months vs >24 months)
- subjects by ibrutinib treatment duration (< 24 months vs >24 months), excluding those who discontinued ibrutinib due to PD

FACT-Lym Total score change from baseline by visit will be presented for:

- subjects who discontinued ibrutinib for any reason other than PD vs. who did not discontinue ibrutinib
- subjects who discontinued ibrutinib for any reason other than PD after achieving BOR of SD or PR vs. CR

FACT-Lym Total score change from baseline by visit will be descriptively presented with the categorical effects including only subject comparison, visit, and subject comparison-by-visit interaction.

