5.2. Study Treatment

- All eligible subjects for randomization will be treated with rituximab in combination with either ibrutinib (Arm A) or matching placebo (Arm B) according to the dose and schedule outlined in [Table 2](#).
- Treatment with ibrutinib or placebo, referred to as study drug, will continue until disease progression, unacceptable toxicity, withdrawal of consent for treatment, or study end, whichever comes first. All subjects treated in this study will follow guidelines for dosing and toxicity management as described in [Section 5.3.1](#) and [Section 5.3.2](#) of the protocol for study drug (ibrutinib/placebo) and rituximab, respectively.

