Caution must be exercised not to confuse a possible tumor flare with progressive disease. Delayed responses after a tumor flare have been reported in follicular lymphoma. In order to accommodate the potential for immune flare (pseudoprogression), treatment with study drug (ibrutinib/placebo) and/or rituximab (if ongoing) may continue between the initial assessment of suspected progression and confirmation of progression. Subjects with radiographic PD who, in the Investigator's opinion, continue to receive clinical benefit from their treatment may continue to receive study treatment as dictated in the protocol after consultation with the Medical Monitor and at the Investigator's discretion. In the absence of clinically significant deterioration, a CT scan or biopsy may be performed at least 4 weeks later to confirm PD. If PD is confirmed at the later time point, PD should be assigned to the prior time point at which PD criteria were also met. Study treatment should be discontinued if there is confirmed PD per Revised Criteria for Response Assessment of Malignant Lymphoma ([Cheson 2014](#)).

Refer to [Appendix G](#) for response criteria.

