**Table 6. Definitions and Analyses for Endpoints**

Endpoint	Definition	Analysis Method
Primary Endpoint		
PFS assessed by investigator	
Time from the date of randomization to the date of the first documented disease progression (PD) or death due to any cause, whichever occurred first, prior to the initiation of subsequent anti-cancer therapy, regardless of premature discontinuation of study treatment. Stem cell transplant is not considered a subsequent anti-cancer therapy for PFS.
 
For the evaluation of disease progression, an adequate post-baseline assessment is defined as an assessment where there is enough evidence to indicate the subject had or had not progressed based on Cheson 2014 (Lugano Classification Criteria).
 
Subjects without baseline or post-baseline disease assessment will be censored at the date of randomization.
	
Primary Analysis:
 
Subjects without a PFS event will be censored at the date of the last adequate post-baseline assessment showing no evidence of PD.
 
Stratified log-rank test is the primary analysis comparing treatment effects. Cox proportional hazards model stratified by the pre-specified stratification factors will be used to estimate hazard ratio (HR) and its associated confidence interval (CI). In addition, Kaplan-Meier estimates and median PFS with its associated CI will be displayed. Brookmeyer-Crowley confidence interval based on the log-log-transformed Greenwood variance estimate will be calculated for median PFS (mPFS); KM estimates at selected landmark points will also be provided.
 
Handling strategies to address intercurrent events in Section 1.2.1 will be implemented.
 
Primary Analysis Censoring Rules
 
 
A. Treatment policy strategy will be used to handle the intercurrent events of discontinuation of study treatment; i.e ignore the intercurrent events and use time to PD or death, whichever occurs first regardless of discontinuation of study treatment.
 
B. Hypothetical strategy will be used to handle the intercurrent events of subjects who received anti-cancer treatment; i.e. subjects who initiated subsequent anti-cancer treatment will be censored at the last adequate post-baseline disease assessment showing no evidence of PD before the use of subsequent anti-cancer therapy.
 

 An AbbVie Company	PCYC-1141-CA Analysis Study Statistical Analysis Plan	Page 20 of 33

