ORR assessed by investigator	The proportion of subjects achieving a best overall response of CR or PR based on Cheson 2014 (Lugano Classification Criteria) per investigator assessment at or prior to initiation of subsequent anti-cancer therapy. Subjects who did not have any post-baseline disease assessments or initiated subsequent anti-cancer therapy prior to initial CR/PR will be considered non-responders when summarizing ORR.	
CMH chi-square test controlled for the pre-specified stratification factors, rate ratio and 95% CI.
 
Sensitivity Analysis:
 
ORR by IRC: same analysis as above.
 
A forest plot will be provided for subgroups.

DOR	DOR is defined as the time from initial CR or PR to PD or death due to any cause, whichever is first reported, regardless of discontinuation of study treatment. If such event does not occur, then subjects will be censored at the last adequate disease assessment as required for PFS censoring.	
Duration of response (DOR) by investigator: Kaplan-Meier estimates and associated CIs.
 
Censoring rules for DOR will follow the censoring rules as the PFS primary analysis for US and Other Regions, respectively.
 
Sensitivity Analyses:
 
Same as the PFS sensitivity censoring rules for US and Other Regions, respectively.
 
DOR by IRC: same analysis as above

OS	Time from the date of randomization to the date of death from any cause. Subjects who are not known to have died will be censored at the last known alive date.	
Efficacy analysis is similar to the PFS primary analysis. Unstratified log-rank test, unstratified Cox regression model to estimate HR and its associated CI will be applied if the stratification factors selected for the PFS primary analysis do not warrant stratified analysis. Kaplan-Meier estimates, median OS, and associated CI. A forest plot will be provided for subgroups.
 
Supplementary analysis:
 
 
• censor subjects who died due to COVID-19 at the day prior to the death date.
 

Endpoint	Definition	Analysis Method
Rate of infusion related reaction	Proportion of subjects experiencing infusion related reactions (IRR) that start on the day of a rituximab infusion and are assessed as related or possibly related to rituximab.	Chi-square test, rate ratio and 95% CI. For each treatment, Clopper-Pearson method is used for 95% CI of the estimated rate.

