## 5.2 Exploratory Safety Analyses

TEAE summaries will be presented by yearly intervals for both treatment arms using the prevalence of new and ongoing events during each ibrutinib/placebo treatment duration interval (> 0-1 years, > 1-2 years, > 2-3 years, > 3-4 years, > 4-5 years, > 5-6 years, > 6-7 years) and for the overall TEAE period. Specifically, the treatment duration interval > 0-1 years includes all subjects who received ibrutinib/placebo treatment up to 1 year; > 1-2 years includes all subjects who received ibrutinib/placebo treatment more than 1 year and up to 2 years, etc.

For the determination of yearly prevalence, newly occurring TEAEs in the respective treatment duration yearly-interval as well as TEAEs still ongoing from the previous treatment duration yearly-interval will be included. Ongoing events for a subject from previous time period are only included in the next time period when the subject is at risk (i.e. within 30 days of last ibrutinib/placebo dose date) at the start of the next time period.

The prevalence of TEAEs will be summarized across yearly-intervals by MedDRA SOC and PT for all TEAEs, grade 3 and higher TEAEs, SAEs and TEAEs related to ibrutinib/placebo.

In addition, all TEAEs by SOC and PT will be summarized across yearly intervals for the following:

- subjects who discontinued ibrutinib for any reason other than PD vs. who did not discontinue ibrutinib
- subjects who discontinued ibrutinib for any reason other than PD after achieving BOR of SD or PR vs. CR

TEAEs leading to death will be summarized by SOC and PT at the study-duration yearly interval when the subject died. Study duration is considered instead of treatment duration in order to include events that started prior to 30 days after ibrutinib/placebo discontinuation, and for which death may have occurred outside of that time period.

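### The exploratory splits by ibrutinib duration and discontinuation in SAP 4.1 group subjects on post-baseline status tied to progression, so longer treatment looks beneficial even if duration has no effect

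*SAP*

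**What the plan says.** SAP 4.1 opens its list with "Analyses of PFS, DOR, TTP, and DOCR for the following". Three of its four items matter here:

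- ibrutinib duration below against above 24 months, in all subjects;
- the same split restricted, as "subjects by ibrutinib treatment duration (< 24 months vs >24 months), excluding those who discontinued ibrutinib due to PD";
- "subjects who discontinued ibrutinib for any reason other than PD vs. who did not discontinue ibrutinib".

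The clocks are defined in SAP Table 6. For PFS: "Time from the date of randomization to the date of the first documented disease progression (PD) or death due to any cause". TTP also runs from randomization. For DOR: "DOR is defined as the time from initial CR or PR to PD or death due to any cause". DOCR starts at first CR.

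Protocol 5.2 ties duration to outcome, since study drug "will continue until disease progression, unacceptable toxicity, withdrawal of consent for treatment, or study end, whichever comes first". Protocol 7.2 gives a limited exception: "Subjects with radiographic PD who, in the Investigator's opinion, continue to receive clinical benefit from their treatment may continue to receive study treatment".

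Neither SAP 4.1 nor Table 6 specifies a landmark, a time-dependent covariate or a descriptive-only caveat for these time-to-event comparisons. The SAP revision history shows that they came in with the v6.0 addendum of 17 April 2024 and were carried into v7.0. Their stated purpose is to assess further the efficacy and cumulative safety of ibrutinib as the protocol gives it.

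SAP 5.2 tabulates TEAE prevalence by yearly treatment interval. It explains membership with wording such as "> 1-2 years includes all subjects who received ibrutinib/placebo treatment more than 1 year and up to 2 years". It then carries ongoing events into the next interval only for subjects at risk when that interval starts, meaning within 30 days of the last dose.

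**The concern.** Treatment duration is known only after follow-up that already contains the endpoint. A subject in the group above 24 months must have stayed on drug for 24 months, and so was essentially progression-free throughout. That time is guaranteed event-free for one group and not for the other. For DOR the guaranteed stretch is 24 months less the time to first response.

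The restricted split adds a second fault. PD is an event of all four endpoints, and subjects who stopped because of PD are deleted. The discontinuation comparison has a related fault. Group membership depends on what happened during follow-up, and PD stoppers fall in neither group. Non-PD discontinuers, by contrast, stay in response follow-up and their later progressions count.

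At stake is the question the analyses were added to answer. Output that favours longer treatment by construction could be read as support for treating until progression.

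**Working it through.** **Inputs from the documents.** Control median PFS 28 months, HR 0.60, 200 events, one-sided 0.025 (SAP 1.3); 3:1 allocation (SAP 1.6.2); 440 planned subjects, so Arm A is 0.75 × 440 = 330; PFS primary analysis expected at about 77 months (Protocol 10.3); enrollment complete by 1 July 2021 (SAP 1.3), about 34 months before SAP v7.0.

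**Check on the design inputs.** The SAP gives no figure for the exploratory analyses, so the stated power of about 87% serves as the check. By Schoenfeld's formula, power = Φ(|ln 0.60| × √(200 × 0.75 × 0.25) − z). Here 0.5108 × 6.124 = 3.128. With z = 1.960, Φ(1.168) = 87.9%; at one-sided 0.024 it is 87.5%. Both agree with the SAP.

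**Immortal time by hand.** Arm A median = 28 / 0.60 = 46.7 months; hazard = ln 2 / 46.7 = 0.01485 per month. P(event by 24 months) = 1 − exp(−0.01485 × 24) = 0.30, or about 99 of 330 subjects. None of them can enter the longer group unless treated beyond PD. True 36-month PFS is exp(−0.01485 × 36) = 0.586. The longer group shows 0.586 / 0.700 = 0.837, purely because nobody in it can fail before month 24.

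**Simulation with no duration effect** (400,000 Arm A subjects per scenario). PFS time T is exponential with median 46.7 months. Non-PD stopping time D is exponential with rate −ln(1 − r)/12 for yearly rate r. Cutoff C is uniform on 35-77 months. Duration = min(T, D, C). A PD stopper has T ≤ D and T ≤ C, with PD rather than death as the event. A one-covariate Cox model compares above with below 24 months. Assumed, because the documents do not give them: r of 5%, 15% or 30%; deaths as 0%, 20% or 40% of PFS events; the follow-up spread; no treatment beyond PD; stopping independent of prognosis.

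| r | Deaths | HR, all subjects | HR, PD stoppers excluded | PFS events removed by exclusion | Landmark HR, PD stoppers kept | Landmark HR, PD stoppers excluded |
|---|---|---|---|---|---|---|
| 5% | 0% | 0.132 | 0.056 | 90% | 0.990 | 0.081 |
| 5% | 20% | 0.133 | 0.101 | 72% | 1.013 | 0.310 |
| 5% | 40% | 0.132 | 0.116 | 54% | 1.001 | 0.507 |
| 15% | 0% | 0.252 | 0.152 | 73% | 0.997 | 0.224 |
| 15% | 20% | 0.255 | 0.202 | 59% | 1.011 | 0.409 |
| 15% | 40% | 0.253 | 0.224 | 44% | 1.003 | 0.571 |
| 30% | 0% | 0.361 | 0.259 | 54% | 1.000 | 0.386 |
| 30% | 20% | 0.361 | 0.298 | 43% | 0.996 | 0.523 |
| 30% | 40% | 0.362 | 0.324 | 32% | 1.002 | 0.655 |

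As Kaplan-Meier estimates in all subjects, 36-month PFS is about 84% in the longer group against 16%, 33% and 46% in the shorter group at r = 5%, 15% and 30%. In 2,000 trials of 330 subjects per r with 20% deaths, an unadjusted log-rank test on either split favoured longer treatment in essentially every run. The landmark with PD stoppers kept rejected in 4.8-5.1% of runs at two-sided 5%. The last column shows that a landmark alone is not enough; PD stoppers must also be kept.

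**The case against.** The analyses are labelled exploratory and lie outside the tested sequence of PFS, ORR, OS and infusion-related reactions. SAP 4.1 names no hazard ratio or test for these splits, and Table 6 gives Kaplan-Meier estimates with confidence intervals for DOR, TTP and DOCR. This stands: the harm is misreading of supportive output, and the hazard ratios above only express its size. The Kaplan-Meier curves are distorted in the same way.

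The landmark result near 1.0 also depends on stopping being unrelated to prognosis. With a shared frailty (assumed log-hazard coefficients of 0.7 for PFS and 0.5-1.0 for stopping) and still no duration effect, the landmark hazard ratio was about 0.73 to 0.58. This stands too: a landmark removes immortal time but not confounding by the reason for stopping.

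Three stronger readings are tempting, and the documents do not support them:

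- **Adverse events share the 24-month split.** They do not. SAP 4.1 applies it only to the four efficacy endpoints, and one of its two versions keeps PD stoppers.
- **The yearly TEAE table is shown to be biased.** SAP 5.2 already has an at-risk rule, and the simulation contains no adverse events. What exists is an inconsistency of wording.
- **The group that did not discontinue has no PFS events.** This holds only if every event is PD or every on-treatment death counts as a discontinuation. Protocol 9.2 does not list death as a reason for stopping treatment, and Protocol 7.2 allows some treatment beyond PD. With on-treatment deaths counted in that group, and deaths assumed at 20-40% of PFS events, its event share was 22-56%, against about 37-43% among non-PD discontinuers.

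**Conclusion.** The point holds for the two 24-month splits of PFS, DOR, TTP and DOCR. With no true effect of duration, the plan as written gives an apparent PFS hazard ratio of about 0.13-0.36 in all subjects. Excluding PD stoppers gives 0.06-0.32, further from 1 in every scenario. The sizes depend on the assumed stopping rate, death share and follow-up; the direction was the same in all nine scenarios. Treatment beyond PD was not modelled and would loosen the link somewhat.

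The comparison of non-PD discontinuers with subjects who did not discontinue conditions on post-baseline status and omits PD stoppers. The direction and size of its distortion depend on how on-treatment deaths are classified, so no figure is claimed.

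In SAP 5.2 the fault is one of definition. Read literally, the interval sentences form disjoint groups by total duration, yet carrying an event into the next interval requires a subject to belong to both. The primary PFS result and type I error control are unaffected.

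**What to change.** 1. Replace both duration splits with a 24-month landmark analysis. Include subjects who are event-free for the endpoint concerned and in follow-up at 24 months, group them by on or off ibrutinib at that time, count PFS, DOR, TTP and DOCR from the landmark, and keep subjects who later stop for PD. This also places subjects with exactly 24 months of treatment, who now fall in neither group.
2. Replace the non-PD discontinuation comparison with a Cox model in which non-PD discontinuation is a time-dependent covariate and PD stoppers are kept.
3. State that both are descriptive and that confounding by the reason for stopping remains.
4. In SAP 5.2, define each yearly denominator as all subjects still on ibrutinib/placebo, or within 30 days of the last dose, at the start of the interval, and reword the interval sentences to match.

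The cost is SAP wording and the programming of exploratory tables. The price in information is a smaller set: for PFS under the design assumptions, about 0.70 × 330 = 231 Arm A subjects reach the landmark. Of these, 1 − 0.95² = 10% to 1 − 0.70² = 51% (about 23 to 118) would be off ibrutinib for non-PD reasons at the assumed stopping rates, so the off-drug group could be small.
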